3.2 Study Design

This is a phase 3B multicenter, randomized, double-blind, active-controlled study designed to evaluate the CV safety of febuxostat compared with allopurinol in subjects with gout and significant CV comorbidities. Approximately 7500 subjects will be randomly assigned to study drug treatment.

The overall duration of the study is dependent on the number of predefined MACE. The length of the study is expected to be approximately 9 years. The length of study participation for each subject will vary due to the event driven study design. This study is designed to have a maximum of 624 MACE.

On Study Day 1, eligible subjects will be randomized in a 1:1 ratio to receive either febuxostat once daily (QD) or allopurinol QD. Randomization will be stratified based on baseline renal function (normal renal function or mild renal impairment versus moderate renal impairment). Baseline renal function will be defined using the following criteria based on estimated creatinine clearance (eCLcr):

- Normal renal function: defined as an eCLcr ≥ 90 mL/min.
- Mild renal impairment: defined as an eCLcr 60 to 89 mL/min, inclusive.
- Moderate renal impairment: defined as an eCLcr 30 to 59 mL/min, inclusive.

where estimated creatinine clearance (eCLcr) is calculated using the Cockcroft-Gault formula corrected for ideal body weight (IBW); IBW is 50 kg for males and 45.5 kg for women, plus 2.3 kg for each inch in height >5 feet (60 inches)]:

[figure not shown]
$$eCLcr = \frac{(140 - \text{Age}[\text{yr}]) \times (\text{IBW}[\text{kg}]) (\text{women multiply by } 0.85)}{72 \times (\text{serum creatinine} [\text{mg/dL}])}$$

Subjects randomized to febuxostat will initially receive the 40 mg dose QD. Subjects will remain on 40 mg for the remainder of the study if their serum uric acid (sUA) is <6.0 mg/dL at the Week 2 Visit. If their sUA is ≥ 6.0 mg/dL at the Week 2 Visit they will receive febuxostat 80 mg QD at the Week 4 visit, and will remain on this dose for the remainder of the study.

Subjects randomized to allopurinol who have normal renal function or mild renal impairment will initially receive allopurinol 300 mg QD with the dose increased in 100 mg increments monthly until either a sUA <6.0 mg/dL or an allopurinol dose of 600 mg QD is achieved. Subjects randomized to allopurinol who have moderate renal impairment will initially receive allopurinol 200 mg QD with the dose increased in 100 mg increments monthly until either a sUA

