6.6 Study Drug Exposure and Compliance

Summaries of study drug exposure, study participation, and compliance will be presented by treatment group and based on the FAS. No inferential statistics will be presented.

A subject's extent of drug exposure will be calculated as the duration of treatment in the double-blind treatment period. Duration of study drug exposure in days will be defined as (date of last dose - date of first dose + 1). If the date of last dose is missing and a subject has discontinued from the study, then, for summary purposes, the last dose date will be estimated as the last drug dispense date plus the number of days in the dosing interval or date of last contact, whichever comes first. The study participation will begin on the day of randomization and end on the day of last contact. Duration of study participation in days will be defined as (date of last contact - date of randomization + 1). For subjects who report a MACE event after treatment discontinuation, the start date of the event will be used as the date of last contact.

Treatment duration and study participation will be summarized overall and by treatment group using descriptive statistics and subject counts at the intervals: Day 1 to Day 364 [Year 1], Day 365 to Day 728 [Year 2], Day 729 to Day 1092 [Year 3], Day 1093 to Day 1456 [Year 4], Day 1457 to Day 1820 [Year 5], Day 1821 to Day 2184 [Year 6], and \geq Day 2185 [\geq Year 6]. In addition, within each treatment group, the duration of treatment by each dose will be summarized.

Study drug compliance will be calculated and summarized with descriptive statistics and subject counts within compliance categories (<80%, 80–<90%, \geq 90%). Compliance (%) will be calculated as the number of capsules taken divided by two times the number of days on drug.

The number and percentage of subjects on the final dose and with dose adjustment from initial dosing will be summarized by treatment group. The final doses based on sUA response and by baseline renal function are summarized in [Figure 3.a](#).

The number and percentage of subjects with use of each type of prophylactic medication based on the initial dosing and dose adjustment from initial dosing will be summarized by treatment group. In addition, descriptive statistics on the total number of days (date of last dose - date of first dose + 1) of prophylactic dosing will be summarized by treatment group.

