6.7.1 Efficacy Endpoints

There are no primary or secondary efficacy endpoints in the study. However, the following efficacy related other endpoints will be summarized.

- Percentage of subjects whose average sUA levels from the end of the first year of treatment to the end of the study are <4.0 mg/dL, ≥ 4 to <5.0 mg/dL, ≥ 5 to <6.0 mg/dL, and ≥ 6.0 mg/dL.

Average sUA will be computed based on all post-baseline sUA values collected from the end of the first year of treatment to the end of the study. For subjects with at least a year of study treatment exposure, all sUA values up to 1-day after a subject's last dose of study drug will be included in the analyses.

- The mean number of flares requiring treatment from the end of the first year of treatment to the end of the study.

The flare rate from the end of the first year of treatment (≥ 365 Days) to the end of the study will be summarized. Flare rate will be calculated as the number of flares from the end of the first year of treatment to the end of the study divided by the length of time on treatment during the period after the first year and through the end of study. The flare rate and 95% CI will be computed using Poisson regression model adjusted for treatment exposure with average sUA category as a factor in the model.

For subjects with at least a year of study treatment exposure, all flares up to 30 days after a subject's last dose of study drug will be included in the analyses.

- Percentage of subjects with tophi resolution by in Years 1, 2, 3, 4, 5, 6, and 7 for subjects with a primary palpable tophus at the Day 1 Visit.

For subjects with a primary tophus at baseline (Day 1 assessment), the percentage of subjects with tophi resolution at the end of Years 1, 2, 3, 4, 5, 6, and 7 of treatment will be summarized. The estimate for tophi resolution rate will be calculated using the life-table method. In calculating the percentage of subjects with tophi resolution, yearly intervals will be used in the life-table analysis. All tophus data up to 30 days after a subject's last dose of study drug will be included in the analyses.

The time intervals that will be used in the life table method relative to the first day of study drug and steps to calculate the resolution rate at the end of each interval are summarized in [Table 6.b](#).

Table 6.b Time Intervals and Steps to Calculate Tophus Resolution Rate

Time Interval (Years)	Interval Number	n_t	r_t	w_t	n'_t	P_t

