0 – 1	1	n_1	r_1	w_1	$n'_1 = n_1 - \frac{w_1}{2}$	$P_1 = 1 - Q_1$
1 – 2	2	$n_2 = n_1 - r_1 - w_1$	r_2	w_2	$n'_2 = n_2 - \frac{w_2}{2}$	$P_2 = 1 - Q_2$
2 – 3	3	$n_3 = n_2 - r_2 - w_2$	r_3	w_3	$n'_3 = n_3 - \frac{w_3}{2}$	$P_3 = 1 - Q_3$
3 – 4	4	$n_4 = n_3 - r_3 - w_3$	r_4	w_4	$n'_4 = n_4 - \frac{w_4}{2}$	$P_4 = 1 - Q_4$

For $t = 1, 2, 3, 4$, n_t is the number of subjects who have not had a resolved primary tophus at the beginning of the t^{th} interval, r_t is the number of subjects whose tophus resolved during the t^{th} interval, w_t is the number of subjects who were censored or lost during the t^{th} interval, n'_t is the number of subjects who have not had a resolved primary tophus at the end of the t^{th} interval adjusted for early withdrawal, and P_t is resolution rate at the end of the t^{th} interval.

$Q_t = \prod_{i=1}^t (1 - r_i/n'_i)$ is the conditional probability of no resolution at the end of the t^{th} interval, where \prod is the product notation.

In addition, the relationship between average serum urate concentration and occurrence of any gout flare requiring treatment (at least 1 occurrence versus no occurrence) from the end of the first year of treatment to the end of the study will further be evaluated using logistic regression model adjusting for baseline sUA. Descriptive summary of the baseline and average post-baseline sUA values will also be provided by occurrence of any gout flare (at least 1 occurrence versus no occurrence).

The following additional gout flare summaries will also be performed. The windows convention for the gout flare summaries by 6 month intervals [days] are: ≤ 6 [Days 2 to 182], 6-12 [Days 183 to 364], 12-18 [Days 365 to 546], 18-24 [Days 547 to 728], 24-30 [Days 729 to 910], 30-36 [Days 911 to 1092], 36-42 [Days 1093 to 1274], 42-48 [Days 1275 to 1456], 48-54 [Days 1457 to 1638], 54-60 [Days 1639 to 1820], 60-66 [Days 1821 to 2002], 66-72 [Days 2003 to 2184], 72-78 [Days 2185 to 2366], and 78-84 [Days >2366]. All flare data collected from baseline and up to 30 days after a subject's last dose of study drug will be included in the analyses.

- The number and percentage of subjects requiring treatment for gout flare will be summarized by prophylaxis medication use and overall by 6 Month intervals. A subject who reports more than one flare during the same time interval will be counted only once for that time interval.

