- The total number of flares and the flare rate per subject year of treatment exposure will be summarized by 6 month intervals. Within the time intervals, subject year is the total number of days of drug exposure for all subjects with exposure for the interval divided by 365.
- The number and percentage of subjects requiring treatment for gout flare will also be summarized by signs and symptoms of gout flare (Swelling, Redness, Tenderness, Joint Warmth, and Other Signs/Symptoms).

If a subject reports more than one signs and symptoms category, then for summary purpose the subject will be counted within each reported signs and symptoms category. However, if a subject reports the same signs and symptoms more than once during the study period then the subject will be counted only once in that category. Summary in each signs and symptoms category will also be provided by severity level (Mild, Moderate, Severe). If a subject reports different severity level for the same signs and symptoms category during the study period, the most severe level will be used for summary purposes.

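### The flare rates count 30 days after the last dose that their denominator leaves out; the Poisson interval and the any-flare model need smaller, conditional repairs (minor)

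*SAP*

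**What the plan says.** Section 6.7.1 defines two sets of flare rates.

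- **Post-year-1 rate.** The count takes in "all flares up to 30 days after" the last dose, for subjects with at least a year of exposure. It is "divided by the length of time on treatment during the period after the first year and through the end of study". The rate and its 95% CI are "computed using Poisson regression model adjusted for treatment exposure with average sUA category as a factor in the model".
- **6-month rates.** The count uses "All flare data collected from baseline and up to 30 days after" the last dose. In the denominator, "subject year is the total number of days of drug exposure for all subjects with exposure for the interval divided by 365".

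Section 6.6 settles what exposure means: "Duration of study drug exposure in days will be defined as (date of last dose - date of first dose + 1"). It has no 30-day extension.

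Section 6.7.1 also relates average sUA to the occurrence of any flare after year 1. That relation "will further be evaluated using logistic regression model adjusting for baseline sUA"; no term for time at risk is named. Section 3.2 says of follow-up: "The length of study participation for each subject will vary due to the event driven study design".

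These are additional endpoints. Section 6.7 presents them by achieved sUA level and not by treatment group, and section 6.7.1 says that there are no primary or secondary efficacy endpoints.

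**The concern.** A rate needs the same window above and below the line. Here the numerator runs up to 30 days longer than the denominator, so the error can only be upward. In the 6-month rates, a flare can even fall in an interval to which its subject contributes no time. Take a last dose on day 540 and a flare on day 555. The flare is inside the 30-day window and falls in the interval of days 547 to 728, but the subject's exposure ended in the interval of days 365 to 546.

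Two further features bear on the same outputs. A Poisson model with no stated handling of overdispersion gives intervals that are too narrow when some subjects flare much more often than others. A yes/no flare outcome with unequal follow-up can mix urate level with length of treatment.

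At stake is how well the trial describes flare frequency and its relation to urate, and nothing beyond that.

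**Working it through.** The SAP gives no flare rate, dispersion or post-year-1 exposure, so there is no planned figure to reproduce. The windows and the exposure definition come from sections 6.6 and 6.7.1. Everything else below is assumed. The 10% annual drop-out in section 5.0 is a planning figure for MACE, and section 3.2 keeps following subjects who stop study drug. Stopping of study drug was therefore varied at 5%, 10% and 20% a year.

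**1. Window mismatch, one subject.** With a constant flare rate and T years on drug after year 1, the overstatement is (30/365)/T, and 30/365 = 0.0822.

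| T (years) | Overstatement |
|---|---|
| 1 | 8.2% |
| 2 | 4.1% |
| 4 | 2.1% |

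**2. Window mismatch, pooled, early stoppers only.** Each year on drug yields about h stops, and each stop adds up to 30/365 of a year of uncounted time. The excess is about h × 30/365.

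| Stopping per year | h × 30/365 | Simulated, post-year-1 rate |
|---|---|---|
| 5% | 0.4% | 0.4–0.5% |
| 10% | 0.8% | 0.8–1.0% |
| 20% | 1.6% | 1.6–2.0% |

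The 6-month rates give the same 0.4%, 0.8% and 1.6%. At 10% a year, about 4.9% of subjects stop in an interval and mean exposure is 177.5 days: 0.049 × 30 / 177.5 = 0.8%.

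The ratio of the flare rate at ≥6.0 mg/dL to that at <4.0 mg/dL does not change if stopping is unrelated to sUA. If the stopping hazard rises 1.6-fold per mg/dL, the ratio moves by at most 1.2% at 10% a year and 2.3% at 20% a year.

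**Simulation inputs (all assumed).** 4000 subjects, 200 replicates per scenario; 0.4 flares a year; average sUA mean 5.6, SD 1.1; baseline sUA mean 8.7, SD 1.5, correlation 0.3; post-year-1 follow-up uniform on 1.5–4 or 1.5–6 years; flare rate ratio 1.0, 1.1 or 1.3 per mg/dL; stopping hazard ratio 1.0, 1.3 or 1.6 per mg/dL; gamma dispersion k of 0, 1 or 2.

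**3. Poisson interval.** With flare rate r and equal exposure T, the variance is inflated by 1 + k·r·T. At r = 0.4 and T = 2.5:

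- k = 1: 1 + 1.0 = 2.0, so the true SE is 1.41 times the Poisson SE. Coverage is 2Φ(1.96/1.41) − 1 = 83%.
- k = 2: 1 + 2.0 = 3.0, so the ratio is 1.73 and coverage is 74%.

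Unequal exposure raises the ratios to about 1.5 and 1.9, with coverage near 81% and 70%. Simulated mean coverage over the four sUA categories was 94–96% at k = 0, 77–87% at k = 1 and 63–78% at k = 2. A robust variance gave 93–97%.

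**4. Any-flare logistic model.** The chance of at least one flare is 1 − exp(−rate × time), so time at risk enters directly. Simulated odds ratios per mg/dL, with stopping at 10% a year:

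| Stopping hazard per mg/dL | No true relation | True rate ratio 1.1 |
|---|---|---|
| unrelated to sUA | 1.00 (rejection 4–5%) | direction holds |
| ×1.3 | 0.91–0.96 | 1.02–1.07 |
| ×1.6 | 0.84–0.93 | 0.96–1.01 |

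A true rate ratio of 1.3 stays positive even at ×1.6 (1.10–1.26). An odds ratio is not a rate ratio, so only the null value and the sign are compared. A Poisson model with robust variance and continuous sUA recovered 1.00, 1.10 and 1.30 in all scenarios, with null rejection of 3–7%.

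**The case against.** **The 30-day convention is open and used throughout.** The 6-month rate is labelled as per subject-year of treatment exposure. Section 6.12.3 (MACE per 100 patient-years) and section 6.12.4 (adverse events per 100 subject-years) likewise set events up to 30 days after the last dose against days on treatment. This is true, and it means that flares should not be changed alone. But disclosing a convention does not make the two windows agree.

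**The tail may hold few recorded flares.** Section 3.2 describes phone contact every 2 months after study drug is stopped, and does not say that flares are collected in those calls. This stands. It limits the size of the bias, and it means that adding tail days to the denominator could push the rates too low.

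**A reader might infer a pooled excess of 2.4% to 4.2%** by giving every subject a full tail. That needs flares to be recorded after the final dose in subjects who complete the study. The SAP describes no such collection, so that range is not claimed.

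**Poisson regression need not mean an uncorrected variance.** The SAP does not state the variance method, and it does not say that flares are overdispersed. Without overdispersion the interval is sound. The point is therefore a cheap safeguard and not a proven error.

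**The logistic model is only a further look.** The Poisson model already adjusts for exposure. This also stands. A reader might infer that the logistic result is biased because follow-up varies. Varying follow-up alone does not do that: stopping must depend on sUA, which the SAP does not state. Large odds ratios from comparing fixed follow-up times, such as 2.65 for 1 against 2 years at 0.5 flares a year, illustrate the mechanism and are not estimates for this trial.

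**Conclusion.** Minor. The mismatch between flare count and denominator is wrong as written and needs no assumption to establish. Its size does: about 0.4% to 2% pooled over early stoppers, assuming constant flare rates, stopping of 5% to 20% a year and flares recorded in the tail. It is larger for single subjects with short exposure after year 1.

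The Poisson point is a conditional improvement. Coverage is about 63% to 87% if dispersion is 1 to 2, and about 95% if there is none. The logistic point is secondary, and matters only if stopping of study drug is related to sUA.

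It would be wrong to conclude that the urate-flare relation is unreliable or that the safety conclusions are touched. The non-inferiority analysis of MACE uses none of these models.

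**What to change.** 1. **Windows.** For the post-year-1 and the 6-month flare rates, end the flare count at the last dose. Alternatively, and only where flares were actually collected after the last dose, add those observed at-risk days (up to 30) to the denominator. Ending the count is the safer choice, because it does not depend on post-dose capture. Align the rates in sections 6.12.3 and 6.12.4, or state why they differ.
2. **Variance.** Name Poisson regression with robust or scaled variance, or negative binomial regression. The price is wider intervals if flares are overdispersed: standard errors about 1.4–1.6 times as large at dispersion 1, and 1.7–2.1 times at 2.
3. **Urate-flare relation.** Make the exposure-adjusted count model with robust variance the main analysis, with continuous average sUA and baseline sUA as covariates. Keep the logistic model as descriptive. A complementary log-log model with a time-at-risk offset is not a good replacement. With dispersion 2 and a ×1.6 stopping hazard, its null rejection reached 30% at 10% stopping a year and 46% at 20%.

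The cost is SAP wording and a few lines of code on data already collected.

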6.5.1 Gout Disease History

Summaries of gout disease history will be presented by treatment group and based on the FAS. No inferential statistics will be presented.

Descriptive statistics will be provided for continuous variables (baseline serum urate, years with gout, total number of tophi at baseline, pain scale rating of last gout flare). The number and percentage of subjects will be presented by treatment group for the following categorical variables: baseline serum urate (<7.0, 7.0–<8.0, 8.0–<9.0, 9.0 –<10.0, and \geq 10.0 mg/dL), approximate number of gout flares during the past year (1 to 3, 4 to 6, and >6), time since last gout flare (<1 month ago, 1–<4 Months Ago, 4–<6 Months Ago, 6–<12 Months Ago, and \geq 1 Year Ago), use of previous urate-lowering therapy, signs and symptoms of previous gout flares (Redness, Tenderness, Swelling, Joint Warmth, and Other), pain scale rating of last gout

flare (0 (no pain), 1-5, 6-10), presence of tophus at baseline, and site of primary tophus (wrist/hand, Ankle/Foot/Toe/Instep, Elbow, Knee, and Other).

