6.7 Efficacy Analysis

Efficacy analyses will be summarized by the level of average post baseline sUA achieved using the Full Analysis Set (FAS). The FAS will consist of all subjects who were randomized and received at least one dose of double-blind study medication. The average post-baseline sUA level during the period from the end of the first year of treatment up to 1-day after a subject's last dose of study drug, will be grouped using the following categories <4.0 mg/dL, ≥ 4 to <5.0 mg/dL, ≥ 5 to <6.0 mg/dL, and ≥ 6.0 mg/dL.

Efficacy analyses will not be summarized by treatment group. Since subjects will have their dose of study drug adjusted based on sUA response, the majority of subjects will have sUA values less than 6.0 mg/dL during treatment.

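### The analyses of flares by achieved sUA compare non-randomised groups and use neither prior flares nor tophi, so the estimated relationship is open to confounding by gout severity

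*SAP*

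**What the plan says.** Section 6.7 sets the framework: "Efficacy analyses will be summarized by the level of average post baseline sUA achieved", in four categories from below 4.0 to 6.0 mg/dL and above. It adds that "Efficacy analyses will not be summarized by treatment group".

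Section 6.7.1 then plans two regression analyses of flares from the end of the first year of treatment onward:

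- The flare rate and its 95% CI are computed "using Poisson regression model adjusted for treatment exposure with average sUA category as a factor in the model". No baseline covariate is named.
- A logistic model takes up "the relationship between average serum urate concentration and occurrence of any gout flare requiring treatment", coded as at least one versus none. This "will further be evaluated using logistic regression model adjusting for baseline sUA", and no other covariate is named.

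Section 6.5.1 shows which baseline measures of gout severity are available. The categorical ones include "approximate number of gout flares during the past year (1 to 3, 4 to 6, and >6") and "presence of tophus at baseline, and site of primary tophus". The continuous ones are "baseline serum urate, years with gout, total number of tophi at baseline, pain scale rating of last gout flare".

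Section 6.7.1 also says that the study has no primary or secondary efficacy endpoints. The flare analyses are listed among other endpoints to be summarised.

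**The concern.** A subject's average sUA after Year 1 is an outcome of treatment. It reflects the assigned drug, the titration in the first three months, adherence, and the subject's own disease. Comparing flares across its categories is an observational comparison even though the trial is randomised.

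If gout severity at entry is associated both with the sUA level reached and with later flares, a difference in flare rate between categories will partly, or wholly, reflect severity. The Poisson model has no term that could separate the two. The logistic model has baseline sUA, which is at best a partial proxy for severity. Flare history and tophi bear more directly on flare risk, are already tabulated, and are left out of both models.

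At stake is how far the reported relation between urate control and flares can be relied on. No randomised comparison and no MACE analysis depends on these models.

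**Working it through.** The SAP gives no flare rates, no expected sUA distribution and no correlations, so there is no plan figure to reproduce. What can be checked is the list of model terms and, under stated assumptions, how much confounding those terms would let through.

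**Terms in the models (Section 6.7.1) against available baseline variables (Section 6.5.1)**

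| Variable | Collected at baseline | Poisson model | Logistic model |
|---|---|---|---|
| Baseline sUA | yes | no | yes |
| Flares in past year | yes | no | no |
| Tophus (presence, number) | yes | no | no |

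**Hand calculation, with no true effect of sUA on flares.** All inputs are assumptions. Let p be the share of subjects with severe gout, k their flare rate relative to the rest, a the share of severe subjects averaging 6.0 mg/dL or above, and b the same share among the others.

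- Severe share at 6.0 or above: s1 = pa / [pa + (1 − p)b]
- Severe share below 6.0: s0 = p(1 − a) / [p(1 − a) + (1 − p)(1 − b)]
- Crude rate ratio: [1 + (k − 1)s1] / [1 + (k − 1)s0]

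| p | k | a | b | s1 | s0 | Crude ratio |
|---|---|---|---|---|---|---|
| 0.20 | 2 | 0.35 | 0.25 | 0.07/0.27 = 0.259 | 0.13/0.73 = 0.178 | 1.259/1.178 = 1.07 |
| 0.20 | 3 | 0.40 | 0.25 | 0.08/0.28 = 0.286 | 0.12/0.72 = 0.167 | 1.571/1.333 = 1.18 |
| 0.30 | 3 | 0.50 | 0.25 | 0.15/0.325 = 0.462 | 0.15/0.675 = 0.222 | 1.923/1.444 = 1.33 |

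If a = b, then s1 = s0 and the ratio is 1. If a < b, it falls below 1.

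**Simulation of the planned models.** This used 200,000 subjects, again with no effect of achieved sUA on flares. The assumptions were:

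- severity multiplies the flare rate by 1.5 or 2.0 per SD;
- severity correlates 0.3 with baseline sUA (mean 8.7, SD 1.5 mg/dL);
- achieved sUA has mean 5.3 and SD 1.2 mg/dL;
- the mean flare rate is 0.5 per year;
- time at risk is uniform on 0.5 to 4 years.

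Achieved sUA entered the logistic model as a continuous variable.

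| Correlation of severity with achieved sUA | Poisson rate ratio, 6.0 or above vs below 4.0 | Logistic odds ratio per mg/dL, baseline sUA only |
|---|---|---|
| −0.2 | 0.68 to 0.80 | 0.89 to 0.93 |
| 0 | 1.00 to 1.01 | 1.00 |
| 0.1 | 1.12 to 1.23 | 1.04 to 1.07 |
| 0.2 | 1.26 to 1.47 | 1.09 to 1.13 |
| 0.3 | 1.41 to 1.80 | 1.13 to 1.20 |

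The Poisson contrast is wider than in the hand calculation (top versus bottom category), so the two sets of ratios are not directly comparable. When severity itself is added, every estimate returns to 1.00 or 1.01. Baseline sUA alone does not achieve that in the logistic model. The full correction is a best case, because the simulation adjusts for severity exactly, whereas past-year flares and tophi are only proxies for it.

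**The case against.** The strongest reply is that these are descriptive analyses of additional endpoints, and that a crude exposure-adjusted rate by achieved level is the natural thing to describe. The Poisson model is planned to give rates and CIs. The SAP names no rate ratio and no test, so the ratios above summarise how its rates would compare and are not quantities it says it will report. This stands, and it is the reason to keep the crude rates.

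It does not dispose of the point. The SAP goes on to evaluate a relationship, adjusts that model for one baseline factor, leaves out the more direct severity measures it holds, and says nothing about confounding.

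Three stronger readings are tempting, and the SAP supports none of them:

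- A reader might infer that the plan treats severity as an effect of sUA. It does not: it speaks of a relationship and of summaries, and claims no effect.
- A reader might infer that the bias must exaggerate the benefit of low sUA, because severe gout is harder to control. The SAP gives no data on that association, and dose titration on sUA response (Section 3.2) could weaken it. The direction stays open.
- A reader might take the different adjustment in the two models as a contradiction. It is better seen as a crude summary followed by a partly adjusted model, which is a legitimate sequence.

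**Conclusion.** The point holds as a limited one. Both flare models compare groups defined by a post-randomisation measurement. One has no baseline covariate and the other only baseline sUA, so the estimated relationship is open to confounding by gout severity.

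Neither direction nor size can be settled from the SAP. The range of 1.07 to 1.33 for the crude rate ratio, and the wider simulated range, rest entirely on assumed severity prevalence, flare-rate multiples and correlations. They show that modest associations are enough to create a visible gradient, not that one will occur. The importance is low.

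**What to change.** In Section 6.7.1:

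- Keep the crude exposure-adjusted flare rates by average sUA category.
- Beside them, report a Poisson model that also includes baseline sUA, past-year flare category and presence of tophus at baseline.
- Add past-year flare category and presence of tophus to the logistic model, which already has baseline sUA.
- State that both results are observational associations with achieved sUA.

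Past-year flares need a zero level if zero was recorded. Section 6.5.1 allows a last flare a year or more ago, yet its flare-count categories start at 1. Whether zeros exist in the data cannot be seen from the SAP.

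Randomised treatment is not needed as a covariate for this purpose: randomisation makes it independent of baseline severity except by chance, so it does not address this confounder.

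The cost is a few sentences and variables already tabulated at baseline. A few subjects with a missing baseline item would drop out of the adjusted models, and residual confounding may remain because the covariates are proxies for severity.

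### The tophus life table leaves a death no exit except censoring, so 1 − Q estimates resolution in the absence of death, not the percentage of subjects that the text names

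*SAP*

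**What the plan says.** SAP Section 6.7.1 fixes the method: "The estimate for tophi resolution rate will be calculated using the life-table method", in yearly intervals. It describes the result as "the percentage of subjects with tophi resolution at the end of Years 1, 2, 3, 4, 5, 6, and 7 of treatment".

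Table 6.b has columns for the number at risk (n), resolved (r), withdrawn (w), adjusted number at risk (n′ = n − w/2) and P. The number at risk falls only by r and w, as in n₂ = n₁ − r₁ − w₁. The withdrawal count is defined thus: "w_t is the number of subjects who were censored or lost during the t^{th} interval". Q is the product of (1 − r/n′) over the intervals so far and "is the conditional probability of no resolution at the end of the t^{th} interval"; P = 1 − Q, and "P_t is resolution rate at the end of the t^{th} interval".

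Three further statements set the scope:
- Follow-up for tophi is tied to treatment: "All tophus data up to 30 days after a subject's last dose of study drug will be included in the analyses".
- The definitions under the table cover four intervals only: "For $t = 1, 2, 3, 4$, n_t is the number of subjects who have not had a resolved primary tophus". The text above it asks for seven years.
- Section 6.7 states: "Efficacy analyses will not be summarized by treatment group".

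**The concern.** Death is not named anywhere in the tophus method. A subject who dies with an unresolved tophus is not in r. Unless that subject is to stay at risk after death, the only column left is w. Censoring a subject in a life table amounts to assuming that the tophus would go on to resolve at the rate seen in those still followed. After a death it cannot. The estimator therefore answers one question (how often would tophi resolve if nobody died?) while the label answers another (what percentage of subjects had resolution?).

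The trial enrols subjects with gout and significant cardiovascular comorbidities, so some deaths will occur. Years 5 to 7, which SAP Amendment 2 added, are where the gap between the two quantities is widest. What is at stake is the accuracy of a descriptive percentage in the study report.

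**Working it through.** The SAP states no resolution percentage, so there is no figure to reproduce. The check compares the Table 6.b estimator with a cumulative incidence on the same expected counts.

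**Inputs**
- Withdrawal other than death: 10% per year. This is the drop-out rate in SAP Section 5.0, a sample-size assumption and not a tophus figure.
- Annual on-treatment mortality: not in the SAP. Assumed 1% to 3%, with 0.5% and 5% as outer cases. The 2.8% in Section 5.0 is a MACE rate that includes non-fatal events, so it is not used as mortality.
- Resolution by Year 4 without deaths: not in the SAP. Assumed 30%, 50% or 70% at a constant hazard h = −ln(1 − p)/4, which gives 0.089, 0.173 and 0.301 per year.

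**Formulas**
- (a) SAP rule, deaths in w: P = 1 − Π(1 − r/n′), with n′ = n − w/2.
- (b) Competing risk, only non-death withdrawals in w: P = Σ S₍ᵢ₋₁₎ · rᵢ/n′ᵢ, with Sᵢ = S₍ᵢ₋₁₎ · (1 − (rᵢ + dᵢ)/n′ᵢ), where dᵢ is deaths before resolution.

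**Results, 50% case** (SAP rule against cumulative incidence)

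| Deaths per year | Year 4 | Excess | Year 7 | Excess |
|---|---|---|---|---|
| 0 | 49.9% vs 49.9% | 0 | 70.1% vs 70.1% | 0 |
| 1% | 49.8% vs 49.0% | 0.9 | 70.1% vs 68.2% | 1.9 |
| 2% | 49.8% vs 48.1% | 1.7 | 70.1% vs 66.3% | 3.8 |
| 3% | 49.8% vs 47.3% | 2.5 | 70.1% vs 64.5% | 5.6 |
| 5% | 49.8% vs 45.6% | 4.2 | 70.0% vs 61.0% | 9.0 |

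Excesses are in percentage points, taken before rounding. The SAP rule hardly moves as deaths rise, because it is built to ignore them. At 2% per year the excess in Years 1, 2 and 3 is 0.1, 0.5 and 1.1 points.

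**Range over the 30%, 50% and 70% cases**
- 1% to 3% per year: 0.6 to 3.2 points at Year 4 and 1.4 to 5.9 at Year 7.
- 0.5% per year: at most 0.5 at Year 4 and about 1 at Year 7.
- 5% per year: 2.7 to 5.3 at Year 4 and 6.6 to 9.5 at Year 7.

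**If resolution is mostly early** (assumed hazards 0.5, 0.3, 0.2, 0.1, then 0.05 per year): 1% to 3% mortality gives 0.7 to 2.1 points at Year 4 and 1.0 to 2.8 at Year 7.

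**Closed-form cross-check.** With h = 0.30, death hazard d = 0.02 and t = 7:
- 1 − Q tends to 1 − exp(−0.30 × 7) = 1 − exp(−2.1) = 87.8%.
- The cumulative incidence is h/(h + d) × (1 − exp(−(h + d)t)) = 0.9375 × (1 − exp(−2.24)) = 83.8%.
- The difference is 4.0 points, in line with the expected-count result.

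**The case against.** **Death in w is an inference.** That is true: the definition does not mention death. But the table has no other exit and no competing-event rule is given, so it is the only workable reading.

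**1 − Q is a legitimate estimator, and the fix is also partly hypothetical.** Because tophus data stop 30 days after the last dose, stopping treatment is censored too, and that exit may well be larger than death. With h = 0.30, d = 0.02 and a withdrawal hazard of 0.105 per year, the share who resolve before any exit by Year 7 is 0.30/0.425 × (1 − exp(−0.425 × 7)) = 67.0%, well below both 87.8% and 83.8%. Two parts of this stand: 1 − Q validly estimates resolution without death if censoring is independent, and a cumulative incidence still rests on that assumption for discontinuation. It does not remove the point. A subject who stops treatment could still resolve, whereas one who has died could not, and the label fits neither the estimator nor any stated assumption.

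**Stronger readings that the SAP does not support.** A reader might infer any of the following:
- *That mortality is known to be substantial.* The SAP gives no all-cause rate. Only deaths up to 30 days after the last dose compete here; later ones follow a censoring that has already happened.
- *That the excess is large against its standard error.* The SAP does not give the number of subjects with a tophus. Participation also varies, and administrative censoring would leave few at risk late, so no such ratio is claimed.
- *That the bias differs between the average-sUA groups used for efficacy.* That average starts at the end of Year 1, so subjects who die earlier have none, and nothing in the SAP says that mortality differs by group.
- *That the problem starts at Year 4.* It starts in Year 1 and is merely small there.

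**Conclusion.** The point holds as a mismatch between label and estimator. If deaths are censored, as Table 6.b implies, P overstates the percentage of subjects with resolution from the first year on, by an amount that grows with time. The direction follows from the formulas and needs only that some subjects die before resolution. The size rests on assumptions: roughly 0.6 to 3 points at Year 4 and 1 to 6 at Year 7 for on-treatment mortality of 1% to 3% per year, with the lower part of the Year 7 range if tophi resolve early.

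A related inconsistency needs no assumptions: Table 6.b and its definitions stop at the fourth interval, and the endpoint list in Section 4.3 stops at Year 4, while Section 6.7.1 asks for Years 1 to 7. The Year 5 to 7 figures above extend the stated formula.

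The consequence is low. Section 6.7.1 says that there are no primary or secondary efficacy endpoints, the tophus percentages are not compared by arm, and Section 6.12 limits non-inferiority to the primary safety endpoint. Nothing here bears on the MACE inference.

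**What to change.** In Section 6.7.1:
- Report the cumulative incidence of first tophus resolution at Years 1 to 7 (Aalen-Johansen or its life-table form), with death before resolution, up to 30 days after the last dose, as a competing event.
- Add a column for deaths per interval, separate from w.
- Keep 1 − Q as a supportive estimate, labelled as resolution in the absence of death.
- State that both estimates treat treatment discontinuation as independent censoring.
- Extend Table 6.b and its definitions from four intervals to seven, and bring the list of years in Section 4.3 into line.

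The cost is a few sentences and one standard procedure. Dates of death are already needed for the all-cause death endpoints in Section 4.3. The downsides are that the late percentages come out slightly lower and that the new estimate still depends on the assumption about discontinuation.
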